#### **2.7.1.1: Adverse events during follow up**

Adverse Events Related to RT reported at Follow-up Contact and experienced during follow-up will be summarized. (table 31). Of special interest, the number of patients who reported the vertebral fractures and spinal cord compression will be summarized by treatment arm (table 31b).

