Qualified Investigator
(printed name and signature)

Date

Protocol Number: CCTG SC.24

CENTRE: _____

AMEND #1: 2017-FEB-02; AMEND #2: 2018-APR-03; AMEND #3: 2018-OCT-31

TREATMENT SCHEMA

[figure not shown]
This is a randomized, non-blinded multicentre phase II/III study in patients with spinal metastases.

Stratification

1. Histology (radioresistant[♦] vs. radiosensitive[♦])
2. “Mass”^{*} on imaging (present vs. absent)
3. Centre

[♦] radioresistant are renal cell carcinoma, melanoma, sarcoma and gastro-intestinal; radiosensitive are all other types

^{*} refers to tumour that involves the paraspinal tissues or presence of epidural disease (extra osseous disease extension)

** Standard Conventional Radiotherapy will be referred to as “CRT” throughout this protocol.

*** Stereotactic Body Radiotherapy will be referred to as “SBRT” throughout this protocol.

Primary Endpoint - Phase II

The ability to accrue 54 patients over a 18 month period to a study that randomizes patients with spinal metastases to Stereotactic Body Radiotherapy (SBRT) or Standard Conventional Radiotherapy (CRT) within a Canadian multicentre setting.

Primary Endpoint - Phase III

The primary objective of the phase III study is to assess complete pain response in the treatment area at 3 months post-radiation.

Secondary Endpoints

- Complete pain response in the treatment area at 6 months post-radiation
- Radiation site progression-free survival (RSS PFS) at 3 and 6 months
- Spinal Instability Neoplastic Score at 3 and 6 months
- Overall Survival
- Adverse event profile
- Health-Related Quality of Life
- Economic Analysis
- Radiotherapy Quality Assurance (RTQA) compliance

Tertiary Endpoint

- Radiomics
- Biobanking for future correlative studies

AMEND #1: 2017-FEB-02; AMEND #2: 2018-APR-03; AMEND #3: 2018-OCT-31

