9.1 Evaluation During and After Protocol Treatment

Patients will be evaluated during radiotherapy as well as at 4 weeks, 3 and 6 months after the end of radiotherapy.

| Investigations | | After Treatment |
|--|---|---|
| History and Physical Exam including: | 
 Physical Exam ECOG PS | As per institutional standards, perform if clinically indicated |
| Radiology | 
 MRI entire spine | At 3 and 6 months |
| Pain / Analgesic Assessment | 
 Patient Diary* | At 4 weeks and at 3 and 6 months |
| Adverse Events** | Adverse events \geq grade 2 will be recorded and graded according to the NCI Common Terminology Criteria for Adverse Events (CTCAE) (Appendix V). | During radiotherapy treatment* and post radiotherapy at 4 weeks and at 3 and 6 months |
| Health-Related Quality of Life*** | 
 EORTC QLQ-C30 and QLQ-BM22 questionnaires | At 4 weeks and at 3 and 6 months |
| Economic Analysis**** | 
 EQ-5D-5L questionnaire | At 4 weeks and at 3 and 6 months |
| Other Assessments | 
 SINS score (use scoring sheet**) | At 3 and 6 months |
| Correlative Studies*** | 
 Optional, for consenting patients only: Plasma and Serum | Immediately after the second fraction of protocol therapy |
| 
* See Appendix VII. Worst Pain to be recorded only for the site included in the radiotherapy target volume. The diary MUST capture all medications that affect pain directly (e.g. opioids, non-opioid analgesics) or indirectly (e.g. steroids, co-analgesics) as well as any pre-medications given for the protocol radiotherapy treatment. Other medications may also be listed. Site staff may assist the patient with listing medication names /routes on the diary.
 
** Report only Adverse Events \geq grade 2, using the CTCAE v 4.0. See Appendix V.
 
*** The Quality of Life and Economic Analysis questionnaires will be completed by the patient electronically. See Appendix VI.
 
* Adverse events experienced by the patient during / shortly after radiotherapy treatment, including whether the patient experienced pain exacerbation (Pain Flare) at the treated site, must be evaluated.
 
** See Appendix III.
 
*** See Section 13 and the SC.24 Specimen Collection Manual that is posted on the trial webpage.
 | | |

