14.6 Secondary Endpoint and Analysis

Complete pain response in the treatment area at 6 months post-radiation. All analyses for the primary endpoint will be performed for the complete pain response at 6 months post-radiation.

AMEND #1: 2017-FEB-02; AMEND #2: 2018-APR-03; AMEND #3: 2018-OCT-31

Radiation site progression-free survival (RSS PFS) is defined as the time from the date of randomization to the date of documented local progression, as defined in Section 10.2.2; or the date of death. Patients who have not progressed or died by the cutoff date of final analysis, RSS PFS will be censored on the date of the last disease assessment. A Kaplan-Meier curve for proportions of RSS PFS in each treatment arm will be displayed. The RSS PFS rates at 3 and 6 months and their 95% confidence intervals will be estimated. The 95% confidence intervals for the medial RSS PFS will be computed using the method of Brookmeyer and Crowley. The difference in distributions of RSS PFS in the two treatment arms will be compared using the log-rank test stratified by the stratification factors at randomization except study centre. Other potential important factors that predict RSS PFS will be assessed using Cox regression. Overall survival will be analysed similarly.

The incidence of acute severe adverse incidences for each arm will be calculated with its 95% confidence interval, and the analyses will be performed in a tiered comparison, i.e., comparing the overall incidence rates between treatment arms first, then comparison of radiotherapy and disease related symptoms and compared by means of Chi-square analysis or Fisher exact test.

SINS scores will be summarized for data at baseline, 3 and 6 months evaluations. The potential prognostic effects of baseline SINS score on the complete pain response at 3 months post-radiation and the overall survival will be explored using logistic and Cox regression models respectively.

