## **2.7: Safety**

### **2.7.1: Definitions and variables**

All toxicity/side effects data collected post randomization will be included in the analyses of toxicities.

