**Table 31: Adverse Events/Intercurrent Illness (Worst Ever Grade on study)**

Data set: All Treated Patients (SBRT Arm)						
	Number of patients (%)					Any grade
	N=***					
	Worst grade					
	NR	1	2	3	4	
Patients with any AE	** (**)	** (**)	** (**)	** (**)	** (**)	** (**)
Patients with AE within category						
Category 1 	**(**)	**(**)	**(**)	**(**)	**(**)	**(**)
Event 1	**(**)	**(**)	**(**)	**(**)	**(**)	**(**)
Event 2	**(**)	**(**)	**(**)	**(**)	**(**)	**(**)
Event 3	**(**)	**(**)	**(**)	**(**)	**(**)	**(**)
...						
Category 2 	**(**)	**(**)	**(**)	**(**)	**(**)	**(**)
Event 1	**(**)	**(**)	**(**)	**(**)	**(**)	**(**)
...						

(1) Patients may have more than one event within a category.

**NOTE:** In CRT Arm, the same type of table will be made.

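### SAP 2.7.1.1 words the main adverse-event table as RT-related follow-up events, against the rest of the plan, and the SAP safety section leaves out the intervals and tests in protocol 14.6

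*SAP*

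**What the plan says.** **Scope of the adverse-event summary.** SAP 2.7.1 opens broadly: "All toxicity/side effects data collected post randomization will be included in the analyses of toxicities". SAP 2.7.1.1, which points to Table 31, is narrower: "Adverse Events Related to RT reported at Follow-up Contact and experienced during follow-up will be summarized". The Table 31 shell is headed "Adverse Events/Intercurrent Illness (Worst Ever Grade on study"), uses all treated patients, and begins with a row for patients with any adverse event. It has no relatedness column and no restriction to follow-up.

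Protocol 10.1.4 makes patients evaluable for adverse events from their first treatment. Protocol 9.1 has events of grade 2 or higher recorded during radiotherapy and at 4 weeks, 3 months and 6 months. Its footnote names what sites must assess: "Adverse events experienced by the patient during / shortly after radiotherapy treatment, including whether the patient experienced pain exacerbation (Pain Flare").

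**Inference.** Protocol 14.6 states: "The incidence of acute severe adverse incidences for each arm will be calculated with its 95% confidence interval". It then sets out a tiered comparison, "comparing the overall incidence rates between treatment arms first", followed by radiotherapy- and disease-related symptoms, "compared by means of Chi-square analysis or Fisher exact test". SAP 2.7 and the shells of Tables 31, 32 and 32b have no interval, no named test and no p-value column.

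**Spinal events.** SAP 2.7.1.1 asks for the number of patients with vertebral fracture or cord compression and cites a Table 31b. The only spinal-event shell is Table 32b, which is headed as a count of fractures and of compressions.

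**Blinding.** The protocol's treatment schema says: "This is a randomized, non-blinded multicentre phase II/III study in patients with spinal metastases".

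**The concern.** Two analysts working from this SAP could produce different versions of Table 31. One who follows the sentence in 2.7.1.1 drops events judged unrelated to radiotherapy and events that occurred during it. One who follows the shell, or SAP 2.7.1, keeps both. Pain flare shows what is at stake: sites must evaluate it during and shortly after radiotherapy, yet the SAP never names it.

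The relatedness filter matters because investigators know the arm, and protocol 3.1.2.1 tells them that myelopathy, pain flare and fracture are where SBRT is expected to differ from CRT. Attribution may then differ by arm even if incidence does not. Depending on its direction, that could create a difference in Table 31 or shrink a real one.

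The missing intervals and tests are a separate gap. The adverse event profile is a listed secondary endpoint. The SAP names tests for SINS change, overall survival and quality of life, so silence on safety is not its general style. Counts and percentages alone invite a reader to take imprecision for the absence of a difference.

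**Working it through.** **1. The scope texts side by side**

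| Place | Attribution | Period |
|---|---|---|
| SAP 2.7.1 | none | from randomization |
| SAP 2.7.1.1 | RT-related only | follow-up |
| SAP Table 31 shell | none | on study |
| Protocol 10.1.4 | none | from first treatment |
| Protocol 9.1 | none | during RT and to 6 months |
| Protocol 14.6, first tier | none (overall incidence) | acute |

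SAP 2.7.1.1 is the only entry that filters on relatedness or starts at follow-up. The spinal-event table (SAP 2.7.1.1, Table 32b) and the SAE, fatal and hospitalization rows (SAP 2.7.1.2, Table 32) have no relatedness filter.

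**2. Arm size**

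The plan gives no figure for the safety analysis, so its sample size fixes the denominators. Inputs from SAP 1.1 and 1.2 are 17% versus 34%, two-sided 5%, 80% power and 1:1 allocation. The mean rate is 0.255 and the difference 0.17.

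- Uncorrected n per arm = [1.960·√(2·0.255·0.745) + 0.842·√(0.17·0.83 + 0.34·0.66)]² / 0.17² = 102.0.
- With continuity correction, n = (102.0/4)·[1 + √(1 + 4/(102.0·0.17))]² = 113.5, rounded up to 114.
- Total = 2·114 = 228, the plan's own number.

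**3. Precision at 114 per arm**

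Protocol 3.1.2.1 reports a fracture rate of about 10% for the SBRT regimen. The nearest count is 11/114 = 9.6%.

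- Wilson 95% interval: [p + z²/2n ± z·√(p(1−p)/n + z²/4n²)] / (1 + z²/n), with p = 0.0965, n = 114 and z = 1.96. This is (0.1133 ± 0.0568)/1.0337, or 5.5% to 16.5%. The exact (Clopper-Pearson) interval is 4.9% to 16.6%.
- Exact interval for 0/114: upper limit 3.2%. For 23/114 (about 20%): 13.2% to 28.7%.
- Half-width for a difference, 1.96·√[p₁(1−p₁)/114 + p₂(1−p₂)/114]: 6.8 points at 5% versus 10%, 7.8 at 10% versus 10%, and 9.2 at 10% versus 20%. Apart from the 10% for SBRT, these rates are assumptions.
- Power of a two-sided 5% test: about 30% for 5% versus 10% and 56% for 10% versus 20%. A non-significant test would say little without an interval.

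**4. What differential attribution could do (all inputs assumed)**

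The documents give no attribution rates. Assume the same true all-cause rate of 20% in both arms, and multiply by the share called RT-related:

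| Share called related, CRT / SBRT | RT-related rate, CRT / SBRT | Chance of a significant difference |
|---|---|---|
| 50% / 50% | 10% / 10% | 5% |
| 40% / 60% | 8% / 12% | about 17% |
| 30% / 70% | 6% / 14% | about 52% |

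The range shows sensitivity to the filter. It does not predict what happened at the sites.

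**The case against.** The strongest reply is that the SAP does not clearly limit safety to attributed events. One loosely worded sentence points that way, while SAP 2.7.1 and the Table 31 shell point to all events on study, and a shell that covers intercurrent illness sits badly with an RT-related filter. This stands: the SAP contradicts itself, and the exclusion of events during radiotherapy is one reading of it. The contradiction still needs resolving before the table is programmed.

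A reader might also infer that the whole safety comparison depends on unblinded attribution. The documents do not support that. Fracture, cord compression and serious events are tabulated by arm without a relatedness condition, and fracture is one of the harms investigators would most expect from SBRT. The dependence is confined to Table 31 as worded. The SAE section also defines related broadly, as a link that cannot reasonably be ruled out. If sites use that definition throughout, attribution has less room to differ by arm.

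A reader might infer that the SAP has withdrawn the protocol's safety tests. It has not: it is silent, and SAP 1.3 ties the final analysis to the protocol. But the two-sided 5% convention in SAP 2.3 names no safety test and supplies no interval, so the work is left unspecified.

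The protocol's intervals are per arm and for acute severe events only. It plans none for a between-arm safety difference and none specifically for spinal events. Readers could also compute an interval from the counts and N in Tables 31 and 32, though a planned secondary analysis should not be left to them.

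On Table 32b, the fracture heading may be shorthand for patients, since SAP 2.7.1.1 states that unit. With up to 3 consecutive segments in the target volume (protocol 5.1.2), patients and fractures can differ. This is an ambiguity to clear up; the documents do not show a deliberate change of unit.

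**Conclusion.** The point holds in two parts. First, SAP 2.7.1.1 conflicts with SAP 2.7.1, the Table 31 shell, and protocol 9.1, 10.1.4 and 14.6. If its wording is followed, Table 31 alone omits events during radiotherapy and depends on attribution by unblinded investigators. Second, SAP 2.7 and its shells omit the per-arm 95% intervals for acute severe events and the tiered chi-square or Fisher comparison in protocol 14.6.

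The omitted uncertainty is about 5 to 8 points either side of a single rate of 10% to 20%, and about 7 to 9 points either side of a difference. These figures assume 114 treated patients per arm; the as-treated numbers may differ slightly. The size of any attribution effect cannot be known from the documents.

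The primary pain-response analysis is unaffected. The change should be made because it removes an avoidable source of bias from one table and carries a protocol-specified analysis into the SAP.

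**What to change.** 1. In SAP 2.7.1.1, define the main Table 31 as all collected adverse events (grade 2 or higher) from the first fraction through 6 months, by arm and regardless of attribution. Name pain flare among them. Present RT-related events as a supporting table.
2. Carry protocol 14.6 into SAP 2.7: incidence of acute severe events per arm with 95% confidence intervals, and the tiered chi-square or Fisher comparison with overall incidence first. State the grade and time window that acute severe refers to, since protocol 14.6 gives neither.
3. As an addition to the protocol's plan, have Table 32b count patients with at least one fracture or compression at the treated site, the unit SAP 2.7.1.1 already states. Give 95% intervals for each arm and for the difference.
4. Correct the Table 31b reference to Table 32b.

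The cost is SAP wording and a few table columns. No new data are needed.

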The adverse events anticipated for SBRT are generally the same as for CRT with the exception of radiation myelopathy, pain flare and fracture. Theoretical additional risks associated with SBRT include more intense radiation reactions (e.g. skin, mucosa), which depend upon the radiotherapy field. The most serious risk of spinal SBRT is the occurrence of radiation myelopathy, which can result in permanent paralysis. Recent published guidelines provide safe SBRT dosing to the spinal cord and minimizes this risk to under 5% [[name] 2010; [name] 2013b]; the choice of the experimental arm of this study will account for these. Outcome data utilizing this technique and the published guidelines from the University of Toronto demonstrate good tolerability with no cases of radiation myelopathy [[name] 2013b]. Single institution experience of the study Chair [personal communication [name]] has resulted in no cases of radiation myelopathy in over 1000 treated patients. The second most serious risk is new or progressive vertebral compression fracture (VCF). While this is a known complication of treating bone metastases, its incidence may be greater with SBRT, and has a reported incidence of approximately 10% with the treatment regimen of 24 Gy in 2 fractions. Although VCF is diagnosed post-SBRT, still less than half of all patients require an intervention and, in those that did, a minimally invasive cement augmentation procedure has been applied as opposed to an open spinal surgery. Pain flare may also be more intense with this treatment compared to conventional CRT [Chiang 2013] and may be treated with prophylactic dexamethasone or rescue dexamethasone upon occurrence.

AMEND #1: 2017-FEB-02; AMEND #2: 2018-APR-03; AMEND #3: 2018-OCT-31

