10.2.2 Radiation Site Progression Free Survival (RSS PFS)

Radiation site progression free survival is defined as the time from randomization to local progression or death.

The response assessment will be an investigator interpretation of the following criteria: lesion status, size, epidural disease extent (Bilsky scale and 3 D measurements), degree of angular kyphosis and height of vertebral body [[name] 2015].

Local progression may be defined as:

- Gross unequivocal increase in tumor volume or linear dimension.
- Any new or progressive tumor within the epidural space.
- Neurologic deterioration attributable to pre-existing epidural disease with equivocal increased epidural disease dimensions on MRI.

Biopsy is recommended in those situations in which pseudoprogression due to radiation reaction cannot be ruled out.

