APPENDIX I - PATIENT EVALUATION FLOW SHEET

| Required Investigations | Prior to Randomization | After randomization and prior to 1st fraction of RT | Day 0* | Immediately after 2nd fraction of RT | During RT treatment | 4 wks post-RT | 3 months post-RT | 6 months post-RT |
|--|------------------------|---|--------|--------------------------------------|---------------------|--|------------------|------------------|
| History and Physical | | | | | | | | |
| Physical Exam | ≤ 4 weeks | | | | | As per institutional standards – perform if clinically indicated | | |
| ECOG Performance Status | ≤ 4 weeks | | | | | | | |
| Radiology | | | | | | | | |
| MRI entire Spine | ≤ 8 weeks | | | | | | X | X |
| Pain / Analgesic Assessment | | | | | | | | |
| Patient Diary | ≤ 7 days | | X | | | X | X | X |
| Adverse Events | | | | | | | | |
| Baseline Symptoms / Adverse Events** | ≤ 7 days | | | | X* | X | X | X |
| Health-Related Quality of Life and Economic Analysis | | | | | | | | |
| EORTC QLQ-C30 and QLQ-BM22 questionnaires | ≤ 7 days | | X | | | X | X | X |
| EQ-5D-5L questionnaire | | | | | | | | |
| Other Assessments | | | | | | | | |
| SINS score*** | ≤ 7 days | | | | | | X | X |
| Pregnancy Test | ≤ 7 days | | | | | | | |
| Correlative Studies | | | | | | | | |
| Serum and Plasma Collection** | | X | | X | | | | |
| 
* Day 0 is defined as the day of the first fraction of radiotherapy, but prior to the administration of radiotherapy
 
** Report only Adverse Events ≥ grade 2, using the CTCAE v 4.0. See Appendix V.
 
*** See SINS scoring sheet on Appendix III
 
♦ Evaluation of adverse events experienced by the patient during / shortly after radiotherapy treatment, including whether the patient experienced pain exacerbation (Pain Flare) at the treated site
 
♦♦ See section 13 and the SC.24 Specimen Collection Manual posted on the SC.24 trial webpage.
 | | | | | | | | |

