APPENDIX III - SPINAL INSTABILITY NEOPLASTIC SCORE (SINS) SCORESHEET

| | |
|--|---------------------|
| 
Location
 
 • 3 points: Junctional (C0-C2, C7-T2, T11-L1, L5-S1) • 2 points: Mobile Spine (C3-C6, L2-L4) • 1 point: Semi-rigid (T3-T10) • 0 points: Rigid (S2-S5) | 
Score: _____
 |
| 
Pain relief with recumbency and/or pain with movement/loading of the spine
 
 • 3 points: Yes • 1 point: No (occasional pain but not mechanical) • 0 points: Pain free lesion | 
Score: _____
 |
| 
Bone lesion
 
 • 2 points: Lytic • 1 point: Mixed (lytic/blastic) • 0 points: Blastic | 
Score: _____
 |
| 
Radiographic spinal alignment
 
 • 4 points: Subluxation / translation present • 2 points: De novo deformiye (kyphosis / scoliosis) • 0 points: Normal alignment | 
Score: _____
 |
| 
Vertebral body collapse
 
 • 3 points: > 50% collapse • 2 points: < 50% collapse • 1 point: No collapse with > 50% body involved • 0 points: None of the above | 
Score: _____
 |
| 
Posterolateral involvement of the spinal elements (facet, pedicle or costovertebral joint fracture or replacement with tumour)
 
 • 3 points: Bilateral • 1 point: Unilateral • 0 points: None of the above | 
Score: _____
 |
| 
Sum Score: _____
 | |
| 
Adapted from Fisher 2010. Interpretation:
 
 • Sum Score 0 – 6: Stable • Sum Score 7 - 12: Indeterminate (possibly impending) instability • Sum Score 13 – 18: Instability | |

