### ***1.2 Sample Size Determination***

For the randomized phase II portion of the study, a convenience sample size of 54 patients was considered sufficient to evaluate whether accrual is feasible. This sample size would also provide an opportunity to estimate the CRT and SBRT 3 month complete pain relief response rates, which would provide the basis for the sample size calculation of the future randomized controlled trial.

The final sample size for the phase III part was calculated to detect a 20% improvement in 3 month post-radiation in the complete pain response for patients on SBRT arm to the 20% complete

response rate for patients on the CRT arm. Assuming a 15% drop out/inevaluable rate, we expect the complete pain response rates for the intent-to-treat population to be 17% and 34% for the CRT and SBRT arms, respectively. To detect the difference with 80% power using a 2-sided 5% level test, the sample size is 228. The final data set includes all randomized patients including the phase II and phase III trial phases.

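### The by-arm vertebral fracture summary is framed as reported adverse events, which are collected only from grade 2 up, and the SINS collapse item scored in both arms is not turned into a fracture incidence

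*SAP*

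**What the plan says.** **The fracture count.** SAP 2.7.1.1 opens with "Adverse Events Related to RT reported at Follow-up Contact and experienced during follow-up will be summarized" and then adds that "the number of patients who reported the vertebral fractures and spinal cord compression will be summarized by treatment arm". It cites Table 31b, but no shell has that number. The spinal shell is Table 32b, titled as spinal adverse events. It has columns for the number of fractures and of compressions, at all sites and at treated sites. It gives no data source, fracture definition or denominator.

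**The grade floor.** Protocol 6.0, 9.1 and Appendix I all limit collection: "Report only Adverse Events ≥ grade 2, using the CTCAE v 4.0".

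**The harm.** Protocol 3.1.2.1 ranks new or progressive vertebral compression fracture as the second most serious SBRT risk, at about 10% with the study regimen. It adds that "still less than half of all patients require an intervention". Protocol 3.1.1.1 lists compression fracture as a rare effect of CRT.

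**The imaging-related data.** SINS is scored at baseline, 3 and 6 months in both arms (Protocol 6.0, 9.1 and Appendix I). One of its six items is "Vertebral body collapse", scored 0 to 3 (Protocol Appendix III). SAP 2.5.2.4 and Table 21b summarise the change in each item and compare arms with a Wilcoxon test. Protocol 10.2.2 includes "degree of angular kyphosis and height of vertebral body" among the features that the investigator interprets for local response.

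**The concern.** Protocol 2.3 supports the choice of regimen partly by contrasting a fracture risk of about 10% with 40% for a single-fraction alternative. Readers will probably set the trial's own fracture rate beside those figures, so it matters what the rate counts.

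As framed, it counts what was reported as an adverse event and graded 2 or higher. The trial is not blinded, so the readiness to report a fracture could differ between arms. The collapse item was scored on a fixed schedule without a grade floor, yet the plan never converts it into a number of patients with new or progressive collapse. The safety table could then show fewer fractures than the trial's own records contain, with no way to see the gap.

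**Working it through.** **1. The plan's own figure.** The documents give no sample size, power or expected count for fractures. The only related figure is the total for the primary endpoint: "To detect the difference with 80% power using a 2-sided 5% level test, the sample size is 228". Inputs are 17% and 34%, two-sided alpha 0.05, power 80% (SAP 1.2).

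- Mean rate = (0.17 + 0.34)/2 = 0.255.
- n = [1.960 × √(2 × 0.255 × 0.745) + 0.842 × √(0.17 × 0.83 + 0.34 × 0.66)]² / 0.17² = about 102.0 per arm.
- Continuity correction: (n/4) × [1 + √(1 + 4/(0.17n))]² = 113.5, rounded up to 114 per arm, or 228 in total.

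This matches. With 1:1 allocation, 114 per arm is used below.

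**2. Following a collapse graded 1 through the plan.**

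| Step | Place | Result |
|---|---|---|
| Collected as an adverse event? | Protocol 9.1, Appendix I | No, below grade 2 |
| In a count of reported fracture adverse events? | SAP 2.7.1.1 | No |
| In the SINS collapse item? | Protocol Appendix III | Yes, if the scored category changes |
| Visible as a fracture in a table? | SAP Table 21b | No, only as part of a score-change summary |

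Two ambiguities add to this. SAP 2.7.1.1 speaks of patients, while Table 32b is headed by number of fractures. The opening sentence of 2.7.1.1 is limited to RT-related events, and the text does not say whether that limit applies to fractures.

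**3. Why Table 21b does not give an incidence.** The item scores 0 for none of the listed findings, 1 for more than half the body involved without collapse, 2 for collapse under 50%, and 3 for collapse over 50%. Three different courses give the same change of +1:

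- 0 to 1: more tumour, no collapse;
- 1 to 2: new collapse;
- 2 to 3: progressive collapse.

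If about 10% of patients change and the rest do not, the median change is 0 in each arm. A new-or-progressive fracture rate cannot be recovered from these summaries.

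**4. Illustration of size.** Assumptions: 114 per arm; a true SBRT rate of 10% (Protocol 3.1.2.1); capture shares of 25% to 100%, which are not in the documents. Expected true count = 0.10 × 114 = 11.4.

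| Share reaching the count | Displayed patients | Displayed rate |
|---|---|---|
| 100% | 11.4 | 10% |
| 75% | 11.4 × 0.75 = 8.6 | 7.5% |
| 50% | 11.4 × 0.50 = 5.7 | 5% |
| 25% | 11.4 × 0.25 = 2.9 | 2.5% |

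**5. Unequal capture.** If the true rate were 10% in both arms, with capture of 75% in one and 50% in the other, the table would show 7.5% against 5.0%. That is a spurious 2.5 points, and its sign depends on which arm is captured better.

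**The case against.** Much of the opposing case is sound and limits the point.

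- **The source is not stated.** Table 32b has no grade column and separates treated from other sites. The phase II review in Protocol 14.3 could already report two in-field fractures, and MRI reports are submitted with each follow-up report (Protocol Appendix IV). A separate fracture field outside the adverse-event floor may exist. A reader might infer that fractures come only from grade 2 or higher adverse events; the wording and title point that way but do not prove it.
- **Nothing is lost outright.** Collapse below grade 2 may be absent from the fracture count, but Table 21b keeps the collapse item and compares it by arm with no grade floor or attribution filter.
- **Symptom dependence is not shown.** A reader might infer that the count depends on symptoms, and that better pain relief after SBRT would hide fractures in that arm. Protocol Appendix V only links to CTCAE and gives no fracture grades, and the remark in 3.1.2.1 concerns intervention, not grade.
- **Stored vertebral height is not shown.** Protocol 10.2.2 names height as one input to an investigator's interpretation. The SAP's list of baseline characteristics includes the Bilsky scale and angular kyphosis but not height.
- **The harm is not specific to SBRT.** Protocol 3.1.1.1 lists it for CRT, and both early fractures were on CRT (Protocol 14.3).

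The objection that this is only a matter of format does not stand. A rank comparison of a score that mixes tumour extent with collapse does not answer how many patients had a new or progressive fracture.

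**Conclusion.** The point holds in limited form. As written, the plan can leave fractures graded below 2 out of its by-arm fracture count; it does not state that count's source or denominator, and it does not derive an incidence from the collapse item. The documents do not support saying that fractures are lost, that the count is driven by symptoms, or that it favours a particular arm.

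The size of any undercount is unknown. The fall from 11.4 to between 8.6 and 2.9 patients rests wholly on assumed capture shares, and the 2.5-point false difference on assumed unequal capture. The primary analysis is unaffected. This is a worthwhile, inexpensive improvement to the safety reporting of a harm that the protocol itself ranks highly.

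**What to change.** In SAP 2.7.1.1 and Table 32b:

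1. Add a line for patients whose SINS collapse item moves from 0 or 1 to 2 or 3 (new) or from 2 to 3 (progressive), by 3 months and by 6 months, regardless of adverse-event grade or attribution.
2. Use as denominator the patients with a baseline and a follow-up SINS score, and show those not assessed by arm.
3. Keep reported fracture adverse events of grade 2 or higher as a separate line, and name the data source of each line.
4. State that both lines count patients, and correct the reference from Table 31b to Table 32b.
5. If vertebral body height was stored as data, use it as well.

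**Cost.** SAP wording and one derived variable from data already collected; no new scans or readers.

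**Downsides.** The displayed rate will probably be higher. Progression within the under-50% collapse band is missed unless stored height is available. SINS has no stated blinded review (the blinded central reading in Protocol 13.2 is for RSS PFS), so this removes the grade floor but not assessor unblinding. The scoresheet does not say which segment is scored at follow-up; the derivation assumes that it is the target segment each time, which should be confirmed.
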